3.3.4.1 Laboratory safety assessments

Laboratory test results will be presented descriptively for screening visit and follow-up visit.

3.3.4.1 Physical examination and ECG

Physical exam including ECG results will be presented descriptively for screening visit and follow-up visit.

3.3.4.2 Vital signs and body weight

Height, weight, heart rate and blood pressure will be summarized by descriptive statistics.

3.3.4.3 Local Tolerability

3.3.4.3.1 Subjective injection site discomfort from VAS

VAS will be summarized descriptively for each treatment at each protocol defined time point. VAS will be treated as a continuous variable, so mean, sd, median, minimum, maximum. will be presented.

Additionally, number and % of subjects with score >0 for each treatment at each protocol defined time point will also be presented descriptively.

If there are enough data (i.e., data with score >0), a mixed model will also be applied to comparing the difference between treatment group. Since we may expect few data with score >0, the choice of model will be based on the actual data.

3.3.4.3.2 Injection site discomfort from ordinal pain scales

The discomfort description and duration of discomfort (section 3.2.6.5.2) will be summarized descriptively.

3.3.4.3.3 Erythema and edema

Erythema formation score and edema formation score will be summarized descriptively. These scores will be treated as continuous variables.

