3.2.6.5.3 Draize (Erythema and or edema)

Erythema and edema formation at the site of injection is assessed using the Draize scale shown below:

Erythema Formation		Edema Formation	
Description	Score	Description	Score
No erythema	0	No edema	0
Very slight erythema Barely perceptible	1	Very slight edema Barely perceptible	1
Well defined erythema	2	Well defined edema	2

Moderate erythema	3	Moderate edema Raised approx. 1 mm	3
Severe erythema Beet redness to slight eschar formation	4	Severe edema Raised more than 1 mm and beyond exposure area	4

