3.3 STATISTICAL METHODS

3.3.1 General guideline for descriptive summaries

For continuous variables, mean, standard deviation, minimum, and maximum will be presented for each treatment group.

For categorical variables, count and % of subjects/counts in each treatment group will be presented.

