3.3.4.1 Adverse Events (AE)

All AEs will be coded using the latest Medical Dictionary for Regulatory Activities and summarized descriptively by system organ class and study drug. A summary table indicating the number and the percentage of exposed subjects having at least one AE will be made. A similar table will provide a breakdown of AEs (all and related) by intensity level (mild, moderate, severe).

Note that subgroup analysis is needed for this (section 3.3.5.1)

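### The SAP text plans only mean, SD, minimum and maximum for the 0–4 Draize scores, which do not in general show how many subjects had each grade

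*SAP*

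**What the plan says.** Section 3.2.6.5.3 sets the measurement: "Erythema and edema formation at the site of injection is assessed using the Draize scale shown below". The scale has five grades for each sign, scored 0 to 4. Each grade is defined by a description, ending for erythema at "Severe erythema Beet redness to slight eschar formation".

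Section 3.3.4.3.3 sets the analysis in two sentences: "Erythema formation score and edema formation score will be summarized descriptively", and then "These scores will be treated as continuous variables". It names no assessment time and no count.

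Section 3.3.1 says what the label implies: "For continuous variables, mean, standard deviation, minimum, and maximum will be presented for each treatment group". The alternative in the same section is "For categorical variables, count and % of subjects/counts in each treatment group will be presented", and the Draize scores are not assigned to it.

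For the visual analog scale, section 3.3.4.3.1 plans a continuous summary and then adds a count: "Additionally, number and % of subjects with score >0 for each treatment at each protocol defined time point will also be presented descriptively". The Draize section has no such line.

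**The concern.** The Draize grades are ordered labels. Nothing in the SAP says that the step from grade 1 to grade 2 equals the step from grade 3 to grade 4, and a mean of, say, 0.3 corresponds to no description on the scale. A reader comparing local tolerability wants to know how many subjects on each product had no reaction, a barely visible one, or a well-defined or worse one. That is a set of counts, and the continuous label leads away from it.

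The contrast within the SAP is odd. The 100-mm VAS, for which a mean is natural, also gets a number and % above zero. The five-grade scale, for which counts are natural, gets none.

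What is at stake is the readability of one part of the safety and tolerability comparison, which section 1.2.2 lists as a secondary objective. No test or decision rule is attached to the Draize scores.

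**Working it through.** The SAP gives no Draize figure to reproduce. The check is whether the four statistics of section 3.3.1 determine the number of subjects at each grade.

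**Inputs**
- Grades 0 to 4: section 3.2.6.5.3.
- Statistics: mean, SD, minimum and maximum per treatment, from section 3.3.1.
- N = 85 per treatment: 85 randomized subjects (section 2.1.2) in a two-way crossover, all taken as assessed on both products.
- Grade counts: hypothetical, because the SAP gives none.

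**Formulas.** Let n1 to n4 be the numbers of subjects at grades 1 to 4, and the rest be at grade 0.
- Sum: S = n1 + 2·n2 + 3·n3 + 4·n4
- Sum of squares: Q = n1 + 4·n2 + 9·n3 + 16·n4
- Mean = S/85
- SD = √[(Q − S²/85)/84]

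The planned table therefore carries S, Q, the minimum and the maximum. Two data sets that agree on these look identical in it.

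**Pair 1**
- 0/0/12/1: S = 36 + 4 = 40; Q = 108 + 16 = 124.
- 12/0/0/7: S = 12 + 28 = 40; Q = 12 + 112 = 124.
- Both: mean = 40/85 = 0.471; SD = √[(124 − 1600/85)/84] = √1.252 = 1.119; minimum 0; maximum 4.

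**Pair 2**
- 4/6/0/3: S = 4 + 12 + 12 = 28; Q = 4 + 24 + 48 = 76.
- 6/0/6/1: S = 6 + 18 + 4 = 28; Q = 6 + 54 + 16 = 76.
- Both: mean = 28/85 = 0.329; SD = √[(76 − 784/85)/84] = √0.795 = 0.892; minimum 0; maximum 4.

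**Pair 3, with few reactions**
- 3/0/1/1: S = 3 + 3 + 4 = 10; Q = 3 + 9 + 16 = 28.
- 0/3/0/1: S = 6 + 4 = 10; Q = 12 + 16 = 28.
- Both: mean = 10/85 = 0.118; SD = √[(28 − 100/85)/84] = √0.319 = 0.565; minimum 0; maximum 4.

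What the planned summary leaves open, and counts by grade would show:

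| Grades 1/2/3/4 | Any reaction | Grade ≥2 | Grade ≥3 | Grade 4 |
|---|---|---|---|---|
| 0/0/12/1 | 13 | 13 | 13 | 1 |
| 12/0/0/7 | 19 | 7 | 7 | 7 |
| 4/6/0/3 | 13 | 9 | 3 | 3 |
| 6/0/6/1 | 13 | 7 | 7 | 1 |
| 3/0/1/1 | 5 | 2 | 2 | 1 |
| 0/3/0/1 | 4 | 4 | 1 | 1 |

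**A case where the planned statistics do separate the profiles.** Five subjects at grade 4 and twenty at grade 1 both have S = 20, so both means are 20/85 = 0.235. The sums of squares are 80 and 20, so the SDs are 0.947 and 0.427, and the maxima are 4 and 1. Only the mean fails here.

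**The case against.** The strongest reply is that the planned table contains more than a mean. A reader might infer that a few severe reactions could not be told apart from more numerous trivial ones. The SAP does not support that: section 3.3.1 also requires the SD and the maximum, and five grade-4 reactions against twenty grade-1 reactions differ clearly on both. In very simple cases the counts can even be solved for. With S = 9, Q = 27 and maximum 3, Q equals 3 × S, which is possible only if every non-zero score is 3, so exactly three subjects were affected. This part of the reply stands. What remains is the narrower point that the four statistics do not fix the counts in general.

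It can also be said that ambiguous cases need many reactions, which may be unlikely after a single injection. Pair 3 answers this, since four or five reactions are enough. How many reactions to expect is in any case not stated for this scale.

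Two further replies have some force:
- Adverse events are tabulated by severity: "A similar table will provide a breakdown of AEs (all and related) by intensity level (mild, moderate, severe". A marked local reaction might appear there, but the SAP does not tie those intensity levels to Draize grades, so the table is no stated substitute.
- Section 5 places the planned tables in Appendix 1, which is not shown, and says that structures may change. A reader should not conclude that counts by grade will never be produced, only that the SAP text does not specify them.

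Finally, the output is descriptive, so summarizing an ordinal score by its mean biases no inference. That is true and limits the weight of the point.

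**Conclusion.** The point holds in limited form. Section 3.3.4.3.3 assigns an ordered five-grade scale to the continuous summary, and the text restores no count or % by grade. The number of subjects at each grade, and so the frequency of well-defined or worse reactions per product, cannot in general be read from what is planned. In the worked pairs, identical summaries conceal 1 versus 7 grade-4 reactions, or 2 versus 4 subjects at grade 2 or higher.

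These sizes illustrate what the summary can hide. They are not predictions, because the grade counts are assumed and N = 85 supposes every randomized subject is assessed on both products. The conclusion that the statistics do not determine the counts does not depend on the particular numbers chosen.

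The point is minor. It concerns the presentation of one tolerability measure and has no bearing on the non-inferiority analysis.

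**What to change.** In section 3.3.4.3.3, replace the sentence on continuous variables with wording such as: *Erythema and edema scores will be treated as ordered categories. The number and percentage of subjects at each grade (0 to 4) will be presented by actual treatment received and scheduled assessment, with the number of subjects assessed as denominator. Means and standard deviations may be shown as a supplement.*

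This applies the summary that section 3.3.1 already provides for categorical variables. The proportion at grade 2 or higher then follows by addition. A row for each subject's worst post-dose grade would be useful but is optional. Check that Appendix 1 lists a table that matches.

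The cost is one changed sentence and a longer table. The data are already collected, and no other analysis changes.

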3.3.5 Other statistical Analysis

3.3.5.1 Subgroup Analysis

The following safety and efficacy variables will be summarized descriptively by gender (male, female), age (18.0 – 64.9 years, 65.0 years and above), and race (non-Hispanic Whites, Hispanics, and African-Americans):

- AE (Any)
- Time (min) to glucose >70 mg/dL within 30 minutes of receiving glucagon

This will be done in the ITT population only, and will be done with time based on both “receiving glucagon” and “decision to dose”.

3.3.5.2 Interim Analysis

Interim analysis will not be performed in this study.

4 Data Handling Conventions

4.1 Missing Data

Unless specified in any of the previous sections, no missing data will be imputed.

4.2 REPEATED AND UNSCHEDULED VISIT

Unless specified in any of the previous sections, the principle of 'last observation priority' will be used to handle the situation of a repeated visit.

4.3 PROTOCOL VIOLATIONS

Potential protocol violations are incorporated into the definition of Per Protocol Population (see 3.1.2). This definition excludes from PP analysis any subject who has one of the following 4 major protocol violations:

1. Fails to meet all eligibility criteria.
2. Fails to meet the definition of hypoglycemia steady state prior to dosing at either treatment visit. A steady state of hypoglycemia is defined as two consecutive plasma glucose values between 43.0 and 49.9 mg/dL, and a linearly extrapolated 8-minute later glucose value \geq 42.0 mg/dL.
3. Fails to complete both treatment visits.
4. Fails to receive a dose of both test articles during the study (G-Pen and Lilly Glucagon).

5 PLANED LISTING, TABLE AND FIGURES

Please see the Appendix 1.

Note that this is the planned Table of Contents. Based on the actual data, table numbers, table names and structures may change.

6 SOFTWARE DOCUMENTATION

PC SAS – Windows version 9.1.3 or higher.

PC R - Windows version 12.0 or higher.

WinNonlin - Professional Version 5.2 or higher.

Excel - Microsoft Excel 2007 or higher.

7 APPENDIX

1. Statistical Analysis Plan V2 - Appendix 1 Table of contents V2.xlsx
2. Protocol XSGP-303 v1.2, 29 Jan 2018
3. Protocol XSGP-303 Analytical Data Conventions for Hypoglycemia Induction Procedure, 02 May 2018
4. Protocol XSGP-303 Analysis Populations and Protocol Violations, 03 May 2018
